3 PROTOCOL SYNOPSIS

Trial Number:	2010-03
Title:	Clinical trial of the Edwards Pericardial Aortic Bioprosthesis, Model 11000
Trial Sponsor:	Edwards Lifesciences LLC [name]
Krakow Principal Investigator:	[REDACTED]
Warsaw Principal Investigator:	[REDACTED]
Trial Purpose:	The purpose of this observational trial is to gather further clinical data to confirm the safety and performance of the Edwards Pericardial Aortic Bioprosthesis, Model 11000 in this trial population.
Trial Device:	Edwards Pericardial Aortic Bioprosthesis, Model 11000. An identical valve model, Model 11000A, has labeling that bears the CE marking of conformity under EC Design-Examination Certificate No. 2103732DE04 and CE Marking of Conformity Certificate No. 2103732CE04.
Intended Use:	The Model 11000 valve is intended for subjects who require replacement of their native or prosthetic aortic valve.
Trial Design:	This is a prospective, non-randomized, non-controlled, observational clinical trial. Up to 200 subjects will be enrolled at up to 6 participating trial sites. Each subject is consented for a period of 5 years. All subjects will be assessed clinically at the following intervals: Baseline, Implant, discharge, 3 months, and annually to 5 years.
Population:	Adult subjects diagnosed with aortic valve disease requiring replacement of the native or prosthetic aortic valve.
Enrollment Criteria:	
Inclusion Criteria
 
 • Is 18 years or older • Provides written informed consent prior to trial procedures • Diagnosed with aortic valve disease requiring a planned replacement as indicated in the preoperative evaluation • Scheduled to undergo planned aortic valve replacement with or without concomitant bypass surgery • Geographically stable and agrees to attend all follow-up assessments at the hospital of surgical services for up to 5 years

	
Exclusion Criteria
 
 • Requires emergency surgery¹ • Has prior mitral, tricuspid or pulmonic valve surgery, which included implant of a bioprosthetic valve, mechanical valve, or annuloplasty ring that will remain in situ • Requires multiple valve replacement/repair • Requires a surgical procedure outside of the cardiac area (e.g. vascular bypass) • Has aneurysm of the aortic root and/or ascending aorta requiring surgical intervention • Has active endocarditis/myocarditis or endocarditis/myocarditis within 3 months to the scheduled aortic valve replacement (AVR) surgery • Has renal insufficiency as determined by creatinine (S-Cr) level ≥ 2.5 mg/dL or end-stage renal disease requiring chronic dialysis at screening visit • Has MRI or CT scan confirmed stroke, cerebrovascular accident (CVA) or transient ischemic attack (TIA) within 6 months (180 days) prior to AVR surgery • Has acute myocardial infarction (MI) within 30 days prior to AVR surgery • Has presence of non-cardiac disease limiting life expectancy to less than 12 months • Diagnosed with hypertrophic obstructive cardiomyopathy (HOCM) • Diagnosed with hyperparathyroidism • Exhibits left ventricular ejection fraction $\leq 30\%$ as validated by diagnostic procedure within 30 days prior to AVR surgery • Echocardiographic evidence of an intra-cardiac mass, thrombus, or vegetation • Hemodynamic or respiratory instability requiring inotropic support, mechanical circulatory support, or mechanical ventilation within 60 days prior to AVR surgery • Documented leukopenia ($WBC < 3.5 \times 10^3/\mu L$), acute anemia ($Hgb < 10.0$ gm/dL or 6 mmol/L), thrombocytopenia (platelet count $< 50 \times 10^3/\mu L$) or history of bleeding diathesis or coagulopathy • Diagnosed with myxomatous disease/connective tissue disorders (e.g. Marfan's Syndrome) • Has prior organ transplant • Current or recent participation (within 6 weeks prior to surgery) in an investigational drug or device trial • Was previously implanted with trial device²
--	--

¹ Emergent surgery – surgery is carried out on the referral day before the beginning of the next working day.

² Note: Previously implanted means that the index aortic valve replacement procedure was completed. The procedure is complete when the surgeon takes the subject off cardiopulmonary bypass and restarts the heart.

	
 • Pregnant (female subject of childbearing potential only), lactating or planning to become pregnant during the duration of participation in trial • Currently incarcerated or unable to give voluntary informed consent • Documented history of substance (drug or alcohol) abuse within the last 5 years prior to implant
Trial Endpoints:	
Safety Endpoints:
 
Descriptive information of early rates and late linearized rates of the following:
 
 • Structural valve deterioration • Thromboembolism • All bleeding/hemorrhage • Major bleeding/hemorrhage • All paravalvular leak • Major paravalvular leak • Non-structural valve dysfunction • Endocarditis • Hemolysis • All cause mortality • Trial valve-related mortality • Explant 
Performance Endpoints:
 
 • Clinically acceptable hemodynamic performance confirmed by core lab evaluation of echocardiography • New York Heart Association (NYHA) functional class compared to baseline • Change in Quality of Life questionnaires EQ-5D (EuroQol) and Short Form 12 version 2 (SF-12v2) from baseline/screening to 1-year
Other data:	Blood Data

4 ABBREVIATIONS

ACC	American College of Cardiology	IFU	Instructions for Use
AE	Adverse Event	INR	International Normalized Ratio
AHA	American Heart Association	IRB	Institutional Review Board
AS	Aortic Stenosis	ISO	International Standardization Organization
ASD	Atrial Septal Defect	LVOT	Left Ventricular Outflow Tract
AVR	Aortic Valve Replacement	MI	Myocardial Infarction
CABG	Coronary Artery Bypass Graft	MOF	Multi-system Organ Failure
CBC	Complete Blood Count	MR	Magnetic Resonance
CEC	Clinical Events Committee	NSVD	Nonstructural Valve Dysfunction
CFR	Code of Federal Regulations	NYHA	New York Heart Association
CO/CI	Cardiac Output/Cardiac Index	OPC	Objective Performance Criteria
CRF	Case Report Form	PFO	Patent Foramen Ovale
CV	Critical Value	PMA	Premarket Approval
CVA	Cerebrovascular Accident	POD	Postoperative Day
DIC	Disseminated Intravascular Coagulation	PT	Prothrombin Time
EC	Ethics Committee	PTFE	Polytetrafluoroethylene
eCRF	Electronic Case Report Form	PTT	Partial Thromboplastin Time
ECG	Electrocardiogram	PVL	Paravalvular Leak
EDC	Electronic Data Capture	QOL	Quality of Life
EOA	Effective Orifice Area	RBC	Red Blood Cell
EQ-5D	EuroQol health questionnaire	REB	Research Ethics Board
FDA	Food and Drug Administration	RGA	Returned Good Authorization
FMEA	Failure Modes and Effects Analysis	SAE	Serious Adverse Effect
GCP	Good Clinical Practice	SAR	Specific Absorption Rate
GLP	Good Laboratory Practices	SAVR	Surgical Aortic Valve Replacement
HGB	Hemoglobin	SF-12	Short Form 12 health questionnaire
HIPAA	Health Insurance Portability & Accountability Act	SVD	Structural Valve Deterioration
HCT	Hematocrit	TAD	Tissue Annulus Diameter
HIT	Heparin Induced Thrombocytopenia	TEE	Transesophageal Echocardiography
HOCM	Hypertrophic Obstructive Cardiomyopathy	TIA	Transient Ischemic Attack
ICF	Informed Consent Form	UADE	Unanticipated Adverse Device Effect
ICU	Intensive Care Unit	WBC	White Blood Cell
ID	Identification		
IDE	Investigational Device Exemption		

5 INTRODUCTION

5.1 INTRODUCTION AND BACKGROUND

Valvular heart disease is a life-threatening disease that afflicts millions of people worldwide and leads to approximately 250,000 valve repairs and/or replacements each year. The number of subjects requiring aortic valve replacement (AVR) is increasing due to prolonged life expectancy. Many subjects are asymptomatic until the disease is well advanced and, once diagnosed, have poor prognosis depending on the severity of valve calcification and history of cardiac events.¹ Diseased heart valves can be treated by medication, surgical repair or surgical replacement.

5.1.1.1 AORTIC HEART DISEASE

Aortic valvular heart disease includes conditions involving any of the following – obstructions of the aortic heart valve or stenosis; leakage of the aortic valve, known as regurgitation, incompetence, or insufficiency, and combinations of the two, sometimes referred to as mixed disease or combined lesions. Valvular heart disease may be caused by any number of factors, including congenital abnormalities, infection by various micro-organisms, degenerative calcification and rheumatic heart disease. When subjects become symptomatic, angina, syncope, and congestive heart failure (CHF) are the primary clinical signs observed. Studies report that among symptomatic subjects with medically treated moderate-to-severe AS, mortality rates after the onset of symptoms are approximately 25% at one year and 50% at two years. Other studies show that subjects with symptomatic AS have a life expectancy between 2 – 4 years.² Neither aortic stenosis nor aortic insufficiency can be effectively treated medically; however, the symptoms of aortic valve disease can be managed medically.

5.1.1.2 TREATMENT OF AORTIC VALVULAR HEART DISEASE

Aortic stenosis and insufficiency can be treated by surgical intervention, including balloon valvuloplasty, valve repair, and valve replacement. Balloon valvuloplasty, a treatment option for aortic stenosis, utilizes a balloon-tipped catheter to stretch open the narrowed valve. Valvuloplasty is predominately used to treat children or adults who are poor surgical candidates. Valve repair techniques include annuloplasty for dilated valve disease, patching leaflet perforations, resected vegetations, or tears, and leaflet extension.^{3,4} Aortic valve repair for stenosis does not show good clinical results.⁵ Replacement of the aortic valve is indicated for symptomatic subjects and asymptomatic subjects with left ventricular dysfunction.

5.1.1.3 BIOPROSTHETIC HEART VALVES

Bioprosthetic heart valves are indicated for use in subjects suffering from valvular heart disease. These tissue valves are used particularly in those subjects for whom long-term anticoagulation therapy is contraindicated or who may be difficult to maintain on anticoagulation therapy.

5.2 DEVICE DESCRIPTION

Refer to the *Instructions for Use* in the Clinical Investigator's Brochure (CIB) for a complete description of the device.

The Edwards pericardial aortic bioprosthesis, Model 11000, is a trileaflet bioprosthesis comprised of bovine pericardium that has been preserved in a buffered glutaraldehyde solution and mounted on a flexible frame. It is available in sizes 19, 21, 23, 25, 27, and 29 mm. The bioprosthesis is stored in non-liquid packaging.

The frame is designed to be compliant at the orifice as well as at the commissures. The compliance of the commissure supports is intended to reduce the loading shock at the valve commissures and free margin of the leaflets. The compliance of the orifice is intended to reduce the stress on the leaflets. The compliant orifice concept is based on the physiology and mechanics of natural heart valves and reported experience with implantation of unstented homografts.

The lightweight wireform is made of a corrosion-resistant cobalt-chromium alloy, chosen because of its superior efficiency and fatigue-resistant characteristics, and is covered with a woven polyester fabric.

A thin cobalt-chromium alloy/polyester film laminate band surrounds the base of the wireform frame providing structural support for the orifice. A silicone-rubber sewing ring covered with a porous, seamless polytetrafluoroethylene (PTFE) cloth attached to the wireform frame, which facilitates tissue ingrowth and encapsulation. The aortic sewing ring has been scalloped to conform to the natural aortic root. The compliant nature of the sewing ring facilitates coaptation between the bioprosthesis and an often irregular or calcific tissue bed.

To facilitate implantation in patients with small aortic roots, the Model 11000A has a low profile height. The sewing ring has three, equally spaced black silk suture markers at the cusp centers to aid in bioprosthesis orientation and suture placement.

The Model 11000 bioprosthesis does not require rinsing prior to implantation.

A holder is attached to the bioprosthesis by means of sutures to facilitate handling and suturing the bioprosthesis during implantation. The holder is easily detached by the surgeon.

Edwards Pericardial Aortic Bioprosthesis, Model 11000. An identical valve model, Model 11000A, has labeling that bears the CE marking of conformity under EC Design-Examination Certificate No. 2103732DE04 and CE Marking of Conformity Certificate No. 2103732CE04.

5.2.1 INDICATION FOR USE

The Model 11000 is intended for patients who require replacement of their native or prosthetic aortic valve.

Refer to the *Instructions for Use* in the Clinical Investigator's Brochure (CIB) for contraindications, procedure steps, and cautions.

5.2.2 PRIOR TESTING

A Clinical Investigator's Brochure (CIB) is prepared for the Model 11000; please refer to this document for pre-clinical testing.

5.2.3 PRIOR CLINICAL STUDIES

Twenty (20) subjects are implanted with the Model 11000 Pericardial Bioprosthesis under Version A of this ongoing clinical trial.

A summary of prior clinical studies on similar pericardial valves are included in the Clinical Investigator's Brochure.

6 BENEFITS AND RISKS

6.1 BENEFITS

The benefits of the Model 11000 are assumed the same as other bioprosthetic valves including improved valvular function, acute alleviation of symptoms related to aortic stenosis or insufficiency, and/or improved morbidity and mortality. The additional benefits of this valve are not yet proven.

The anticipated additional benefits of aortic valve, Model 11000 are to eliminate the need for rinsing the index valve prior to implant, less exposure to the risks of glutaraldehyde, and elimination of hazardous waste requiring special disposal.

6.2 RISKS

As with all prosthetic heart valves, serious complications, sometimes leading to death may be associated with the use of tissue valves. Complications due to individual subject reaction to an implanted device, or to physical or chemical changes in the components, particularly those of biological origin, may occur at varying intervals (hours or days) necessitating reoperation and replacement of the prosthetic device. Some or all of the risks listed below could require a reoperation or explant, and/or they may lead to permanent disability or death.

Known/potential risks associated with stented bioprosthetic heart valves include but not limited to:

- Angina
- Bleeding diatheses (coagulopathy) related to anticoagulant therapy
- Cardiac arrhythmias
- Cardiac failure
- Coronary ostial blockage
- Endocarditis
- Hemolysis/Hemolytic anemia
- Hemorrhage
- Immunological response
- Leaflet entrapment (impingement)
- Myocardial infarction
- Nonstructural valve dysfunction
- Paravalvular/Perivalvular leak
- Malfunctions of valve due to distortion at implant, fracture of wireform, physical and or chemical deterioration of valve components
- Patient prosthetic mismatch (PPM)
- Regurgitation/insufficiency
- Stenosis
- Thromboembolism/stroke
- Tissue deterioration including infection, calcification, thickening, perforation, degeneration, suture abrasion, instrument trauma, and or leaflet detachment
- Transient ischemic attack (TIA)
- Valve pannus
- Valve thrombosis

Potential risks associated with aortic valve replacement surgery include but not limited to:

- Allergic reaction
- Annular dissection
- Aortic dissection
- Arterial dissection
- Bleeding, anticoagulant related
- Bleeding, procedural
- Bleeding, post-procedural
- Cardiac arrest
- Cardiogenic shock
- Disseminated intravascular coagulation (DIC)
- Esophageal rupture
- Heart failure
- Hematoma
- Heparin induced thrombocytopenia (HITs)
- Hypotension
- Hypertension
- Hypoxemia
- Infection, local or wound
- Infection, systemic (septicemia)
- Myocardial infarction
- Multi-system organ failure (MOF)
- Pericardial effusion
- Pericardial tamponade
- Pleural effusion
- Pulmonary edema
- Pneumonia
- Renal dysfunction
- Respiratory failure
- Thromboembolism
 - Venous, peripheral or central
 - Arterial, peripheral or central
 - Pulmonary, thrombus or other

Risks associated with Model 11000 are anticipated to be the same as those listed above for other aortic bioprosthetic valves and valve replacement surgery. Based on pre-clinical testing, there are no new risks anticipated with the Model 11000 tissue process or sterilization method.

There may be other unknown risks. All safety events will be collected and reviewed throughout the entire trial and follow-up period. Investigators will be notified of any additional risks identified that could affect the health, safety or welfare of the trial subjects.

7 CLINICAL TRIAL DESIGN

This is a prospective, non-randomized, non-controlled, observational clinical trial. Up to 200 subjects will be enrolled at up to 6 participating trial sites. Each subject is consented for a period of 5 years. All subjects will be assessed clinically at the following intervals: Baseline, Implant, discharge, 3 months and annually to 5 years.

7.1 JUSTIFICATION

This trial is designed to confirm that the performance observed in pre-clinical testing also is observed in the human population.

7.2 PURPOSE

The purpose of this observational trial is to gather further clinical data to confirm the safety and performance of the Edwards Pericardial Aortic Bioprosthesis, Model 11000 in this trial population.

7.3 ENDPOINTS

7.3.1 SAFETY ENDPOINTS

Descriptive information of early rates and late linearized rates of the following:

- Structural valve deterioration
- Thromboembolism
- All bleeding/hemorrhage
- Major bleeding/hemorrhage
- All paravalvular leak
- Major paravalvular leak
- Non-structural valve dysfunction
- Endocarditis
- Hemolysis
- All cause mortality
- Trial valve-related mortality
- Explant

7.3.2 PERFORMANCE ENDPOINTS

The following performance endpoints will be assessed at each scheduled follow-up visit:

- Clinically acceptable hemodynamic performance confirmed by core lab evaluation of echocardiography
- New York Heart Association (NYHA) functional class compared to baseline
- Change in Quality of Life questionnaires EQ-5D (EuroQol) and Short Form 12 version 2 (SF-12v2) from baseline/screening to 1-year

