9 STATISTICAL METHODS

9.1 SAMPLE SIZE

Up to 200 subjects will be enrolled in the trial at up to 6 participating sites.

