9.4 PERFORMANCE ANALYSIS

Hemodynamic Variables

Valvular regurgitation will be summarized by the number and percentage of subjects in each level of regurgitation. Other hemodynamic parameters will be summarized by N, mean, and standard deviation. These summaries will be summarized at baseline and each applicable follow-up visit for all subjects in the investigational valve population, and will be stratified by valve size.

NYHA Class

A comparison of preoperative and postoperative NYHA functional class (presented as the percentage of subjects in each class at baseline, at each follow-up time-point, and as the percentage of subjects at each follow-up time-point who improved, worsened, or did not change in class) will be presented. This comparison will be based on the investigational valve population. Additionally, a cross-tabulation of baseline vs. 1-year NYHA Class will be presented for all subjects in the investigational valve population with both baseline and 1-year NYHA data.

Quality of Life

The number, mean and standard deviation for the Quality of Life (EQ-5D) summary measurement will be presented at the pre-procedure and at the 1-year post procedure follow-up visit. In addition, the number and mean for the change from pre-procedure to the 1-year post procedure follow-up visit will be calculated and presented.

The number, mean, and standard deviation for the SF-12 physical and mental health summary measures (PCS-12 and MCS-12, respectively) will be calculated at the pre-procedure and at the 1-year post procedure follow-up visit. In addition, the number and mean for the change from pre-procedure to the 1-year follow-up in PCS-12 and MCS-12 will be presented.

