		AORTIC: FLOW OBSTRUCTION OF THE AORTIC VALVE DUE TO RESTRICTED LEAFLET OPENING. THE SEVERITY IS CATEGORIZED AS: MILD - JET VELOCITY (M/S) <3.0; MEAN GRADIENT (MMHG) <25; VALVE AREA (CM2) >1.5.MODERATE - JET VELOCITY (M/S) 3.0-4.0; MEAN GRADIENT (MMHG) 25-40; VALVE AREA (CM2) 1.0- 1.5. OR SEVERE - JET VELOCITY (M/S) >4.0; MEAN GRADIENT (MMHG) >40; VALVE AREA (CM2) <1.0; VALVE AREA INDEX<0.6. MITRAL: MITRAL STENOSIS (MS) REFERS TO NARROWING OF THE MITRAL VALVE ORIFICE, RESULTING IN IMPEDANCE OF FILLING OF THE LEFT VENTRICLE IN DIASTOLE. THE SEVERITY OF MS IS CATEGORIZED AS: MILD - MEAN GRADIENT (MM HG) < 5, PULMONARY ARTERY SYSTOLIC PRESSURE (MM HG) < 30, VALVE AREA (CM2) >1.5. MODERATE - MEAN GRADIENT (MM HG) 5-10, PULMONARY ARTERY SYSTOLIC PRESSURE (MM HG) 30-50, VALVE AREA (CM2) 1.0-1.5. SEVERE - MEAN GRADIENT (MM HG) > 10, PULMONARY ARTERY SYSTOLIC PRESSURE (MM HG)> 50, VALVE AREA (CM2) <1.0. TRICUSPID: A NARROWING OF THE TRICUSPID VALVE OPENING THAT INCREASES RESISTANCE TO BLOOD FLOW FROM THE RIGHT ATRIUM TO THE RIGHT VENTRICLE. SEVERE TRICUSPID STENOSIS IS DEFINED AS A VALVE AREA LESS THAN 1.0 CM2.
AE220*	STENOSIS - AORTIC - MILD	"
AE221*	STENOSIS - AORTIC - MODERATE	"
AE222*	STENOSIS - AORTIC - SEVERE	"
AE223	STENOSIS - MITRAL- MILD	"
AE224	STENOSIS - MITRAL - MODERATE	"
AE225	STENOSIS - MITRAL - SEVERE	"
AE226	STENOSIS - PULMONARY- MILD	"
AE227	STENOSIS - PULMONARY - MODERATE	"
AE228	STENOSIS - PULMONARY - SEVERE	"
AE229	STENOSIS - TRICUSPID- MILD	"
AE230	STENOSIS - TRICUSPID- MODERATE	"
AE231	STENOSIS - TRICUSPID - SEVERE	"

AE CODE LIST	
CODE	DEFINITION
AE.6	
CARDIOVASCULAR - THROMBOEMBOLIC EVENT/VALVE THROMBOSIS
 
ANY EMBOLIC EVENT THAT OCCURS IN THE ABSENCE OF INFECTION AFTER THE IMMEDIATE PERIOPERATIVE PERIOD AND MAY BE MANIFESTED BY A NEUROLOGIC EVENT OR A NON-CEREBRAL EMBOLIC EVENT. EMBOLI CONSISTING OF NON-THROMBOTIC MATERIAL (E.G., ATHEROSCLEROSIS, MYXOMA) ARE NOT COUNTED.

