Please indicate whether or not the images were readable:

Was a request sent to the site to resend the images? No Yes

Date of resend request:

Was the readability issue resolved? No Yes

Date readability issue resolved:

Was the ECHO Assessed by the Core Lab? No Yes

Physical Assessment

Height Unit

Weight Unit

Body Surface Area (BSA)

Heart Rate (BPM)

Blood pressure (mmHg) Systolic / Diastolic

Does the Echo indicate the subject has the following cardiac rhythm / conducting system disturbances?

Normal Sinus Rhythm No Yes Indeterminate

Atrial Fibrillation No Yes Indeterminate

Atrial Flutter No Yes Indeterminate

Ventricular Tachycardia No Yes Indeterminate

Ventricular Fibrillation No Yes Indeterminate

AV Block No Yes Indeterminate

Please indicate the degree:

Bundle Branch Block No Yes Indeterminate

Please indicate the branch:

Aortic Valve Assessment: Stenosis

Please indicate the level of Aortic Stenosis:

LV Structure / Regional Function

Please indicate if any of the following abnormalities were observed:

LV aneurysm No Yes

Please specify the location:

Wall motion abnormality No Yes

Please specify:

Cavity dilation No YesApical and/or left atrial thrombi No YesOther abnormality No Yes

Please specify:

Global LV Structure / Function

What method of calculation was used for LV function assessment?

LVEDV (ml):

LVESV (ml):

LVEF (%):

LV Dimensions

Septal thickness (end-diastolic) (cm):

Posterior wall thickness (end-diastolic) (cm):

LV end-diastolic dimension (cm):

LV end-systolic dimension (cm):

LV Mass (g):

BSA corrected LV mass (g/m²):

Aortic DimensionsLVOT Diameter (cm): Aortic annulus (cm): Aortic root diameter (cm): STJ diameter (cm): **Aortic Valve Assessment: Measurements**V_{peakAO} (m/sec): TVI (AO) (cm): Peak systolic gradient of AV (by continuous wave) (mmHg): Mean systolic gradient of AV (by continuous wave) (mmHg): TVI (LVOT) (cm): Maximum V(LVOT) (m/sec): Mean V(LVOT) (m/sec): Stroke Volume (LVOT Derived) (ml): Transvalvular flow (ml/s): Cardiac Output (LVOT derived) (L/min): Cardiac Index (L/min/m²): Aortic EOA (continuity equation) (cm²): Aortic EOA Index (cm²/m²): Performance Index : **Aortic Valve Assessment: Regurgitation**

Please identify all the methods of calculation used:

Color Doppler No YesRegurgitant Fraction No YesProximal Convergent Flow No YesContinuous wave doppler (Pressure half-time) No YesAortic Flow Reversal No Yes

Study Doc#

Subject ID Site Visit Date Status

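### The acceptable-hemodynamics endpoint has no matching analysis for obstruction: gradients and areas are reported only as N, mean and SD, and the core-lab stenosis grade is not tabulated

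*Combined protocol and SAP*

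**What the plan says.** Section 7.3.2 names "Clinically acceptable hemodynamic performance confirmed by core lab evaluation of echocardiography" as the first performance endpoint, to be assessed at each scheduled follow-up visit. Neither the protocol text nor the appendices attach a gradient, area or regurgitation limit to it.

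Section 9.4 treats the two sides of valve hemodynamics differently:

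- Leakage: "Valvular regurgitation will be summarized by the number and percentage of subjects in each level of regurgitation".
- Everything else, including gradients and orifice area: "Other hemodynamic parameters will be summarized by N, mean, and standard deviation".

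These summaries are given by visit and "will be stratified by valve size". For gradients and areas, 9.4 plans no count beyond a limit, no percentiles, no range and no interval.

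The information for a count is already collected. The core-lab result forms in Appendix 15.3 ask: "Please indicate the level of Aortic Stenosis". The Echo Manual (Appendix 15.6) lists a stenosis grade among the core-lab outputs for the TTE and the abbreviated TTE. Appendix 15.1 gives numeric bands for grading aortic stenosis as an adverse event, for example "MODERATE - JET VELOCITY (M/S) 3.0-4.0; MEAN GRADIENT (MMHG) 25-40". Section 9.4 does not tabulate the grade or link it to the endpoint.

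**The concern.** An endpoint about acceptable performance invites the question of how many valves performed acceptably. For leakage, 9.4 lets a reader answer it. For obstruction it does not, because a mean and SD are compatible with very different numbers of poorly performing valves. With no criterion stated in advance, acceptability of gradients and areas would have to be argued from averages once the data are known. The stated purpose is to confirm safety and performance, and a small group of obstructed valves is a finding that such a summary can hide.

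**Working it through.** The plan states no figure to reproduce. Section 9.1 gives only a ceiling ("Up to 200 subjects will be enrolled in the trial at up to 6 participating sites"), with no expected gradient, area or rate. The gradients, areas and SDs below are therefore assumptions. The 25 and 40 mmHg cut-points are the Appendix 15.1 adverse event bands, used for illustration and not proposed as limits.

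**1. How far a few obstructed valves move the mean.** Assume 190 valves at 12 mmHg and 10 valves (5%) at 45 mmHg.

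- Mean = (190 × 12 + 10 × 45) / 200 = 2730 / 200 = 13.65 mmHg, against 12.0 with no obstructed valves. The shift is 1.65 mmHg.

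**2. What the SD does.** The ten valves alone contribute an SD of 33 × √(0.05 × 0.95) = 7.19 mmHg.

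- With an assumed within-group SD of 4: √(16 + 51.7) = 8.2.
- With an assumed within-group SD of 5: √(25 + 51.7) = 8.8.

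The SD roughly doubles, which may alert a careful reader, but it cannot be converted into a count. Take the row mean 13.65, SD 8.2 and ask how many of 200 valves exceed 40 mmHg:

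- normal distribution: (40 − 13.65) / 8.23 = 3.20, tail 0.0007, about 0.1 valves;
- lognormal with the same mean and SD: about 2.7 valves;
- actual number in this example: 10.

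**3. The same point over a range of assumed rows.** Number of 200 valves above 25 mmHg. The last column is the distribution-free ceiling, 200 × SD² / (SD² + (25 − mean)²).

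| Mean, SD (mmHg) | Normal | Lognormal | Ceiling |
|---|---|---|---|
| 10, 4 | 0.0 | 1.0 | 13 |
| 12, 5 | 0.9 | 4.2 | 26 |
| 12, 6 | 3.0 | 7.3 | 35 |
| 15, 6 | 9.6 | 12.9 | 53 |

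For mean 12 and SD 6, the ceiling is 200 × 36 / (36 + 169) = 35.1. For an orifice area below 1.0 cm² with assumed mean 1.6 and SD 0.4, the shares are 6.7% (normal), 3.7% (lognormal) and at most 0.16 / (0.16 + 0.36) = 31%. One reported row thus fits anything from few valves to a substantial share.

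**4. What a proportion would show.** Exact (Clopper-Pearson) 95% intervals:

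- 0 of 200: 0 to 1.8%
- 10 of 200: 2.4 to 9.0%

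The valve comes in six sizes ("It is available in sizes 19, 21, 23, 25, 27, and 29 mm"). With equal strata, an assumption, each holds about 200 / 6 ≈ 33 subjects:

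- 0 of 33: 0 to 10.6%
- 2 of 33: 0.7 to 20.2%

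The overall figure is informative. The by-size figures are coarse but still show where affected valves lie.

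**The case against.** The strongest reply is that the trial is descriptive and uncontrolled, tests no hypothesis, and already covers much of hemodynamics. Several parts of that reply stand.

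- **Regurgitation is counted.** Section 9.4 gives number and percentage by level, so a claim that the plan reports hemodynamics only as averages would be wrong.
- **The Appendix 15.1 stenosis definitions are used.** Stenosis of the study valve is to be reported as structural or non-structural dysfunction, and there are study-valve stenosis codes for mild, moderate and severe. Both categories are safety endpoints, with early percentages, late linearized rates and Kaplan-Meier estimates under 9.3. Ten valves at 45 mmHg would exceed the severe gradient band and could appear there. That route depends on adverse event reporting, is not split by grade, and is not the core-lab endpoint of 7.3.2.
- **Stratification by valve size helps interpretation,** but each stratum is again only N, mean and SD.

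A reader might also infer that the core lab makes an acceptable-or-not call on each valve which 9.4 then ignores. The documents do not support this: the core-lab forms have no such field, and 7.3.2 can be read as a description of the cohort. The only other use of the phrase is a yes/no item on the surgery form, about regurgitation on the post-implant echo. Nor is stenosis graded on every echo: for the implant TEE, the Echo Manual asks the core lab only for leak grades.

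**Conclusion.** The point holds for obstruction. Acceptability is undefined, and 9.4 neither counts valves by gradient or area nor tabulates the stenosis grade that the core lab records. In the assumed example, 5% obstructed valves shift the mean by 1.65 mmHg, and the mean and SD together do not recover the number affected. The example's size rests on assumed gradients; that a mean and SD do not fix a count does not.

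This is a mismatch between endpoint and analysis, with no bearing on sample size or error rates, and should be settled before analysis.

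Two stronger readings should be resisted. One is that the plan cannot address its hemodynamic endpoint at all; the regurgitation table and the dysfunction rates answer that. The other is that the Appendix 15.1 bands are the acceptability limit. They were written for adverse event grading, give no rule when gradient and area disagree, and offer only verbal labels for regurgitation. They also class areas of 1.0 to 1.5 cm² as moderate. With areas assumed normal, SD 0.4, the share below 1.5 cm² is Φ(−0.25) = 40% at mean 1.6 and Φ(−0.75) = 23% at mean 1.8. Whether such valves are acceptable is a clinical choice for the sponsor and core lab.

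**What to change.** In section 9.4:

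1. Add the number and percentage of implanted subjects with a readable TTE in each core-lab stenosis grade, at discharge, 3 months and years 1, 3 and 5, overall and by valve size. State the denominator at each visit.
2. Have the sponsor and core lab fix, before analysis, the criterion for acceptable hemodynamic performance. The Appendix 15.1 bands need not be the limit. Report the percentage meeting the criterion at those visits with an exact 95% interval.
3. Show year 2 and year 4 echoes separately, labelled as a murmur-selected subset. Under the section 10 assessment schedule, an echo is required at those visits only if a murmur is heard, so a percentage there does not describe all implanted subjects.
4. Keep the mean and SD tables and the planned regurgitation table.

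The cost is one extra table from core-lab fields already collected and an advance commitment to a criterion. No new visits, tests or subjects are needed.
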